## 7.5 Measurements of Study Drug Compliance

LOAD703 is given up to 12 times every 3 weeks during the study, while atezolizumab is given continuously every 3 weeks during the study if judged beneficial and safe for the subject by Investigator. The study treatment (LOAD703 and/or atezolizumab) can be omitted, but missed doses will not be made up. Compliance to the study treatment regimen will be determined, separately for LOAD703 and atezolizumab, as the number of doses received divided by the expected number of doses while subject was on-study, multiplied by 100.

Study drug compliance will be summarized using descriptive statistics, by dose group, based on the Safety Population.

## 7.6 Efficacy Evaluation

### 7.6.1 Datasets Analyzed

All efficacy summaries will be based on the Efficacy Evaluable Population per dose group. A data listing of subjects excluded from the Efficacy Evaluable Population, to include the reason for exclusion, will be presented. Efficacy summaries (and corresponding figures) will include all subjects per dose group.

The subjects excluded from each analysis set are described in the Analysis Set Specification.

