## 6 INVESTIGATIONAL PLAN

### 6.1 Overall Study Design

This trial is a multicenter, open label, single arm, dose-escalation Phase I/II trial. The study will have a Bayesian Optimal Interval (BOIN) design ([Ying Yuan 2016](#)) with a target dose limiting toxicity (DLT) rate=0.3 to determine the maximum tolerated dose (MTD) of LOAd703 against a fixed dose of atezolizumab. This design has algorithmic escalation/de-escalation rules like a traditional 3+3 design, but it also allows for specification of the DLT target rate and expanded accrual beyond N=6 with continued and consistent toxicity monitoring. This means that the assessment of DLT rate continues throughout the study, giving a well-defined safety evaluation of the entire study.

[REDACTED]

The total number of subjects to be enrolled in the study to achieve at least 25 evaluable subjects at MTD, should not exceed 50.

[REDACTED]

The trial encompasses a treatment phase ending with last subject last visit (LSLV). For each subject, active participation with study visits is maximum 60 weeks where after they are followed for survival as long as the trial remains open.

After a screening period [REDACTED] each subject will receive a maximum of 12 LOAd703 injections (q3w) in combination with atezolizumab (q3w) after which supportive therapy with atezolizumab alone is continued until the final clinical visits (i.e., maximum 7 additional infusions).

The subjects will be scheduled for study visits until final clinical follow-up in study [REDACTED]. If both treatments are prematurely withdrawn the final clinical follow-up visit could be scheduled earlier, [REDACTED].

[REDACTED]

In total, subjects will visit the clinic regularly for a maximum 60 weeks [REDACTED]. Thereafter only OS will be recorded [REDACTED] whereby information will be collected via telephone calls (US) or medical records (Sweden, US) until death or study end.

The end of the treatment stage is defined as the date of the LSLV and the end of study is defined as LSLV.

The study is initially planned to be conducted at 2 sites in US and 1 site in Sweden. The study has been conducted in 3 sites in US and 1 site in Sweden.

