### 7.1.1 Reporting Conventions

Baseline and safety tables will be summarized by dose group ( $1 \times 10^{11}$  VP LOAd703;  $5 \times 10^{11}$  VP LOAd703). Tables summarizing demographics and other baseline

characteristics will also include a column for all subjects combined (Total). Except where stated, efficacy tables and figures will be summarized for efficacy evaluable subjects by dose. In general, all data collected, and any derived data will be presented in subject data listings for all enrolled subjects. Listings will be ordered by dose group, subject number and assessment or event date. The dose group presented in listings will be based on the planned assignment, unless otherwise noted.

In general,

Non-zero percentages will be rounded to one decimal place. Rounding conventions for presentation of summary statistics will be based on the precision of the variable of summarization, as it is collected in its rawest form (i.e., on the eCRF or as provided within an external file) and are outlined as follows:

- [REDACTED]
- [REDACTED]
- [REDACTED]

Other statistics [REDACTED] will be presented using the same general rules outlined above or assessed for the most appropriate presentation based on the underlying data.

No formal statistical analysis will be performed to compare dose groups. Results will be presented with descriptive statistics will be tabulated by dose group and reviewed to evaluate all study endpoints.

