## 7.2 Analysis Populations

The analysis populations are defined as follows:

- Safety Population: [REDACTED]
- Efficacy Evaluable Population: [REDACTED]

Data summaries to be presented on both the Safety Population and the Efficacy Evaluable Population will only be produced on both analysis sets if there is a difference in the population groups.

Although not formal analysis populations, the following subgroups of subjects are also relevant:

- [REDACTED]
- [REDACTED]
- [REDACTED]

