#### 7.3.2 *Protocol Deviations*

When all subjects have been completed, all data have been entered into the eCRF database, all coding is done and approved, and all queries are solved, the Database Closure procedures will begin. Decisions will be made on how to classify subjects into analysis populations, and how to handle protocol violations and deviating or missing data. All decisions will be dated and documented in a Database Closure document.

All protocol deviations will be listed, and major protocol deviations will be summarized by site (and for all sites combined), protocol deviation category, subcategory, and dose group and over all subjects combined (total).

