#### 7.6.5.6 *Use of an “Efficacy Subset” of Subjects*

No efficacy subset will be used.

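### SAP 7.6.1 restricts all efficacy summaries, including OS, PFS and TTP from first dose, to the evaluable population, while 7.6.1 and 7.6.5.6 also say that everyone is included and no subset is used

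*SAP*

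**What the plan says.** The SAP makes these statements about who enters the efficacy analysis:

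- **7.6.1:** "All efficacy summaries will be based on the Efficacy Evaluable Population per dose group". It then adds: "A data listing of subjects excluded from the Efficacy Evaluable Population, to include the reason for exclusion, will be presented".
- **7.1.1:** "Except where stated, efficacy tables and figures will be summarized for efficacy evaluable subjects by dose".
- **7.6.1, directly after the exclusion listing:** "Efficacy summaries (and corresponding figures) will include all subjects per dose group".
- **7.6.5.6:** "No efficacy subset will be used".

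SAP 7.2 defines a Safety Population and an Efficacy Evaluable Population separately and provides for the case where they differ. Both definitions are redacted. SAP 6.4.2.3 starts TTP, PFS and OS at first dose, and 7.6.4 describes their analysis without visibly naming another population. The Statistical Methods text in protocol section 10 also bases efficacy on patients evaluable for toxicity and response. On classification, SAP 7.3.2 says of the database-closure stage: "Decisions will be made on how to classify subjects into analysis populations, and how to handle protocol violations and deviating or missing data".

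**The concern.** There are two problems.

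First, the instructions conflict as written. A programmer cannot tell from 7.6.1 and 7.6.5.6 whether the efficacy denominator is the evaluable patients or everyone at the dose. The conflict does not come from the redactions, because all the sentences involved are visible.

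Second, on the more explicit reading (evaluable patients only), the restriction extends to OS, PFS and TTP. An evaluable-set response rate is a familiar summary, and the protocol chose it. OS is different: it needs no tumour assessment, so response evaluability gives no visible reason to leave a treated patient out. If evaluability depends on something that happens after first dose, patients who die or stop early leave a survival curve whose clock started at first dose, and early non-responders leave the ORR denominator. Both effects flatter the result. In a small single-arm trial, readers will set these estimates beside external data, so the denominator matters even though nothing is tested.

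**Working it through.** The plan states no figure on this point that could be reproduced, and the efficacy sample-size text (protocol 10.2.2, SAP 7.8.2) is not visible. The check is therefore a comparison of the text, followed by conditional illustrations.

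**1. Text comparison**

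| Question | Points to the evaluable set | Points to all subjects |
|---|---|---|
| Who is in efficacy summaries? | 7.6.1 first sentence; 7.1.1; protocol section 10 | 7.6.1 sentence after the exclusion listing |
| Is a subset used? | 7.2 (separate population, may differ); 7.6.1 (exclusion listing) | 7.6.5.6 |
| Patients with no post-dose scan? | Depends on the redacted definition | 6.4.2.3 and 7.6.5.2 censor them for TTP and PFS at one day after first dose |

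The pooled column in 7.6.3 combines doses. It does not say whether it holds evaluable or all treated patients. SAP 7.9 does not address the conflict.

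**2. ORR, if some treated patients are non-evaluable**

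Assumed: 25 evaluable patients (the planned minimum at MTD), 5 or 8 responders, and 0, 2, 5 or 10 further treated patients without a response. ORR = responders / n, with exact Clopper-Pearson 95% intervals.

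| n | 8 responders | 5 responders |
|---|---|---|
| 25 (evaluable) | 32.0% (14.9 to 53.5) | 20.0% (6.8 to 40.7) |
| 27 treated | 29.6% (13.8 to 50.2) | 18.5% (6.3 to 38.1) |
| 30 treated | 26.7% (12.3 to 45.9) | 16.7% (5.6 to 34.7) |
| 35 treated | 22.9% (10.4 to 40.1) | 14.3% (4.8 to 30.3) |

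With 8 responders the shift is 2.4 to 9.1 percentage points; with 5 it is 1.5 to 5.7.

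**3. OS, if evaluability required survival to time t**

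Assumed: exponential survival, S(x) = 0.5^(x/median), with deaths before t excluded and nobody else. Then 12-month OS in the subset = S(12)/S(t). Nine weeks is used as the central case because protocol 7.5.1 schedules imaging every ninth week: t = 63 / (365.25/12) = 2.07 months.

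| True median OS | t | S(12) / S(t) | 12-month OS in subset | True 12-month OS |
|---|---|---|---|---|
| 12 months | 6 weeks | 0.500 / 0.923 | 54% | 50% |
| 12 months | 9 weeks | 0.500 / 0.887 | 56% | 50% |
| 12 months | 12 weeks | 0.500 / 0.853 | 59% | 50% |
| 8 months | 9 weeks | 0.354 / 0.836 | 42% | 35% |
| 18 months | 9 weeks | 0.630 / 0.923 | 68% | 63% |

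Under this model the subset median is the true median plus t. A 12-month median reads 13.4 to 14.8 months for t of 6 to 12 weeks.

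**4. PFS and TTP under the same kind of rule**

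PFS counts death as an event, so dropping early deaths inflates it as it does OS. For TTP, an unscanned patient is censored at one day after first dose and adds almost nothing to the curve, so excluding such a patient changes little.

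**5. The null case**

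If the evaluable and safety populations contain the same patients, every difference above is zero.

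**The case against.** **The conflict may be loose drafting.** Protocol section 10 displays response statistics for patients treated at MTD. The second statement in 7.6.1 could therefore mean all evaluable patients at each dose, not only at MTD. Section 7.6.5.6 sits among template headings and could mean no subset beyond the 7.2 populations. Both readings are plausible, but the text states neither. Adopting them also confirms that OS and PFS are confined to evaluable patients.

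**A reader might infer that OS and PFS suffer immortal-time bias.** The documents do not support that as fact. The membership rule is redacted. Protocol 7.5 frames response assessment by what patients receive, which suggests an exposure criterion. The censoring rule for patients with no post-dose scan suggests that such patients may be in the set. If a single early dose suffices, the effect could be near zero.

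**A reader might take the enrolment limit as evidence of exclusions.** SAP 6.1 says that enrolment "to achieve at least 25 evaluable subjects at MTD, should not exceed 50". Under the protocol's Definition of Terms, however, a patient is enrolled on signing consent. The 50 therefore includes screen failures and patients at the other dose. It says nothing about how many treated patients at MTD will be non-evaluable.

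**A reader might infer that populations will be chosen once responses are known.** SAP 7.3.2 is loosely worded, but 7.2 does contain a definition, 7.6.1 refers to an Analysis Set Specification, and the SAP is to be final before database lock. Nothing says that closure decisions override the definition.

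**A flat statement that no all-treated efficacy result is planned would go too far.** Parts of 7.6.3 and 7.6.4 are redacted, and 7.1.1 leaves room for exceptions. Against that, the first sentence of 7.6.1 allows none.

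**Transparency and status.** Exclusions are listed with reasons, all deaths are listed, and data are listed for all enrolled subjects, so all-treated figures could be rebuilt from the listings. Safety is primary, and efficacy is secondary and descriptive. This limits the harm, but it does not say which denominator the headline tables will use.

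**Conclusion.** The point holds, with moderate confidence, in two parts that rest on visible text. The SAP contradicts itself on the efficacy population. Its most explicit rule confines OS, PFS and TTP to an evaluable set that may be smaller than the treated set, with no all-treated alternative in view.

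The size of any bias is conditional. It requires a membership rule that depends on exposure, survival or imaging after baseline, and at least one treated patient who fails it. Under the stated assumptions, ORR moves by about 2 to 9 points and 12-month OS by about 4 to 9 points. The responder counts, numbers excluded, survival medians and landmark times are all assumptions, not figures from the plan. No formal test and no documented figure is affected; what is at stake is how the efficacy estimates are read.

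**What to change.** 1. In SAP 7.6.1, name one population per endpoint. Analyse OS, PFS and TTP in the Safety Population by dose, and confirm that its redacted definition means all treated patients.
2. Report ORR and CBR in all treated patients, with non-evaluable patients counted as non-responders, beside the evaluable-set figures that the protocol calls for.
3. Align 7.1.1, 7.6.1 and 7.6.5.6 with that choice. If the second statement in 7.6.1 means all evaluable patients at both doses, say so.
4. State in 7.3.2 that decisions at database closure only apply the definition already written in the SAP.

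The cost is small: existing tables are repeated on an existing population, with no new data. The all-treated ORR will be equal or lower whenever the excluded patients have no response, and the sponsor should expect that.

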### 7.6.2 Primary Efficacy Endpoint Analysis Methods

There is no primary efficacy endpoint in this study.

### 7.6.3 Secondary Endpoint Analysis Methods

A summary of BOR, ORR and CBR based on the derivation of BOR which includes MR will also be produced. In addition to columns for each dose, an additional column including all subjects (irrespective of dose received) will be included.

[REDACTED]

[REDACTED]

[REDACTED]

[REDACTED]

#### 7.6.4 *Other Efficacy Endpoint Analysis Methods*

Time to event variables (TTP, PFS and OS) will be summarized as follows:

The number and percentage of subjects with an event and being censored will be presented. Kaplan-Meier product-limit estimates for the 25th percentile, median and 75th percentile will be presented with 95% CIs. The range of values (both including and excluding censored values) will also be presented. The estimated survival distribution function and the number of subjects at risk at 3-month intervals (i.e., 3, 6, 9, months etc) for TTP/PFS or 4-month intervals (i.e., 4, 8, 12, months etc) for OS will be presented.

Kaplan-Meier plots will also be produced.

[REDACTED]

- [REDACTED]

• [REDACTED]

[REDACTED]

[REDACTED]

[REDACTED]

onders [REDACTED] g [REDACTED]

## 7.6.5 *Statistical/Analytical Issues*

### 7.6.5.1 *Adjustments for Covariates*

There are no planned applications of covariate adjustments; all statistical results are descriptive in nature.

### 7.6.5.2 *Handling of Dropouts or Missing Data*

For the purpose of calculating time since initial melanoma diagnosis, partial diagnosis dates will be imputed as follows:

- Missing day only will be imputed with the 1st of the month;
- Missing day and month will be imputed with 1st January.

No imputation will be done if the diagnosis date is completely missing.

If the imputed date is after the date of informed consent, the date of informed consent will be used instead (i.e., a time since diagnosis will be computed as 1 day).

The analysis of TTP and PFS will censor subjects without events at the date of the last evaluable tumor assessment. If a subject does not have any evaluable post-dose tumor assessments, they will be censored at the date of first dose plus 1 day. The analysis of OS will censor subjects without events at the date of last contact.

### 7.6.5.3 *Interim Analyses and Data Monitoring*

There are no interim analyses planned, nor is there a plan to establish a data monitoring committee for this study. The decision to escalate dose will be taken by the Sponsor after a safety meeting including the Sponsor, Clinical Research Organization, Clinical Project

Manager (for taking notes only), Medical Advisor and at least 2 of the site Principal Investigators as a minimum.

#### 7.6.5.4 *Multicenter Studies*

This is a multicenter study, with approximately 3 sites expected to participate. Efficacy data collected from all study sites will be pooled for data analysis. The effect of study site on the efficacy analysis results is not planned to be explored.

#### 7.6.5.5 *Multiple Comparisons/Multiplicity*

There will be no adjustments for multiple comparisons in the efficacy analysis for this study. Results are descriptive in nature and there will be no formal comparisons made among dose groups.

#### 7.6.5.6 *Use of an “Efficacy Subset” of Subjects*

No efficacy subset will be used.

#### 7.6.5.7 *Active-Control Studies Intended to Show Equivalence*

This study does not include an active-control product and is not intended to demonstrate equivalence between any two drug products.

#### 7.6.5.8 *Examination of Subgroups*

ORR will be summarized by the below subgroups:

### 7.7 **Safety Evaluation**

Safety analysis will be carried out for the Safety Population, [REDACTED]. Subjects who do not complete the study, for whatever reason, will have all available data up until the time of termination included in the analysis. For safety analysis presented by study visit, the baseline value will be defined as the last value reported prior to first study drug administration.

#### 7.7.1 *Extent of Exposure*

Extent of exposure to study treatment (LOAD703 and atezolizumab separately) will be summarized for the Safety Population by dose group. The duration of exposure will be presented in days and calculated as the date of last dose of study drug minus the date of first dose of study drug, plus one. Duration of exposure and total number of doses received will be summarized using descriptive statistics. Total dose received (in  $10^{11}$  VP

for LOAd703 and in mg for atezolizumab) will also be summarized. [REDACTED]

[REDACTED] The number and percentage of subjects who had any dose change (either an allowed reduction as per protocol or an unexpected change) will be presented for each drug separately. The number of missed doses will be summarized for both drugs and the number of additional/unplanned doses will be summarized for atezolizumab. A dose is considered missed only if it is followed by a subsequent dose, i.e., doses not administered following permanent discontinuation of a study drug are not considered missed. An additional/unplanned atezolizumab dose is defined as a dose received at [REDACTED].

Study drug administration information will be presented in listings (including any missed doses with reasons for doses being missed).

#### 7.7.2 *Dose Limiting Toxicities*

The number of DLT evaluable subjects ([REDACTED])

[REDACTED] and the total number of DLTs will be presented by dose group. The number and percentage of subjects who experienced at least one DLT and at least one DLT of each severity (grade 3 to 5) will also be presented. Percentages will be based on the number of DLT evaluable subjects. Following the BOPIN principle, isotonic regression using pooled-adjacent-violators algorithm will be utilized to obtain toxicity probability estimates for each dose group and the dose which has the toxicity probability estimate closest to the target DLT rate (0.3) will be defined as the MTD for the study.

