### **5.6.9 LOAD703 Maximum Tolerated Dose (MTD)**

The maximum tested and tolerated dose (MTD) for LOAd703 is defined as the highest safe dose tested in the study based on the BOPIN assessment (see 10.0 STATISTICS).

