## Statistical Methods

Statistics will be displayed for response evaluation for the patients treated at MTD.

75 / 88

Demographic and efficacy analyses will be carried out using all toxicity and response evaluable patients.

Patient disposition, including reason for withdrawal, will be summarized by dose group.

Demographics and disease baseline characteristics, pregnancy test results, medical history and prior medications will be tabulated.

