### 7.8 **Determination of Sample Size**

#### 7.8.1 *Safety*

The study will be conducted using a BOIN design with a target DLT rate of 0.3. This design has algorithmic escalation/de-escalation rules like a traditional 3+3 design but allows for specification of the target DLT rate and expanded accrual beyond N=6 with continued consistent toxicity monitoring (i.e., the assessment of DLT rate continues throughout the study which gives a well-defined safety evaluation of Phase I/II studies).

Two LOAd703 dose levels will be tested together with a fixed dose of atezolizumab. The BOIN design allows for enrollment of 3 subjects in a cohort and the number of subjects with DLT determines whether additional subjects are treated with the current dose or if the dose is decreased or increased. In general, the dose will be escalated if the observed toxicity rate at the current dose is  $\leq 0.2365$ , and the dose will be de-escalated if the observed toxicity rate at the current dose is  $\geq 0.3585$ . If the observed toxicity rate is between 0.2365 and 0.3585, 3 additional subjects will be treated at the current dose. For cohorts of size 3, the decision boundaries are shown below. Additional cohorts will be added in the unlikely event that more than N=25 participants at a single dose level are needed.

Number of Subjects Treated in a Defined Cohort	3	6	9	12	15	18	21	24	25
Escalate dose if number of DLT $\leq$	0	1	2	2	3	4	4	5	5
Treat additional 3 subjects at current dose if number of DLT =	1	2	3	3, 4	4, 5	5, 6	5-7	6-8	6-8
De-escalate dose if number of DLT $\geq^*$	2	3	4	5	6	7	8	9	9
Eliminate** dose level and all higher doses from further use if number of DLT $\geq$	3	4	5	7	8	9	10	11	12

\* At the lowest dose level, if the recommendation is to de-escalate and the dose level has not been eliminated from consideration, 3 additional subjects can be accrued at the same dose level; otherwise, the trial will be stopped.

\*\* Note that if the DLT level reaches the elimination limit, this dose level is abandoned from the study independently of DLT events at lower dose levels.

[figure not shown]

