### 7.8.2 Efficacy

### 7.9 Changes in the Conduct of the Study or Planned Analyses

Section 10.3 of the protocol describes summaries of urinalysis

There were no other changes to the study conduct or planned analyses identified within the development of this SAP, relative to the descriptions provided within the clinical study protocol.

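### The SAP's closest-to-0.3 rule for the MTD does not leave out eliminated doses, has no tie rule, and is not reconciled with the protocol's definition of MTD

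*SAP*

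**What the plan says.** SAP 7.8.1 states the design: "The study will be conducted using a BOIN design with a target DLT rate of 0.3". The escalation and de-escalation boundaries are 0.2365 and 0.3585, and between them the current dose is continued: "If the observed toxicity rate is between 0.2365 and 0.3585, 3 additional subjects will be treated at the current dose". The last row of the table removes a "dose level and all higher doses from further use if number of DLT" reaches a listed count, for example 5 of 9 or 12 of 25. Its footnote adds that "this dose level is abandoned from the study independently of DLT events at lower dose levels". At the lowest dose, elimination stops the trial. Protocol 10.2.1 carries the same table and notes.

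SAP 7.7.2 sets the end-of-study rule. It invokes the BOIN principle, obtains an estimate for each dose group by pooled-adjacent-violators (PAVA), and concludes that "the dose which has the toxicity probability estimate closest to the target DLT rate (0.3) will be defined as the MTD for the study".

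Protocol 5.6.9 says the MTD "is defined as the highest safe dose tested in the study based on the BOPIN assessment" and refers to section 10. The visible text of that section gives boundaries but no selection rule. Protocol 5.1 fixes the actual MTD at the end of the study. Protocol 10.1, under Statistical Methods, adds: "Statistics will be displayed for response evaluation for the patients treated at MTD".

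On departures from the protocol, the visible text of SAP 7.9 mentions urinalysis and then says: "There were no other changes to the study conduct or planned analyses identified within the development of this SAP".

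**The concern.** The sentence in SAP 7.7.2 is the only operational rule for the MTD, and it is silent in three places.

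- It takes its candidates from every dose group, so a dose withdrawn under SAP 7.8.1 still competes.
- With two doses, PAVA gives both the same estimate whenever the observed rate at dose 1 is at least that at dose 2. The rule then names no single dose.
- It is not tied to the wording of Protocol 5.6.9. The two can point to different doses when dose 2 ends in the de-escalate or eliminate rows and dose 1 has few DLTs.

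At stake is which dose carries the MTD label. If the gap is left open, it will be settled after the DLT counts are known, which is the kind of post hoc decision the SAP says it is written to avoid.

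**Working it through.** **Inputs.** From SAP 7.8.1: target 0.3, the boundaries, the nine-column table and two doses. From SAP 7.7.2: PAVA and the closest-to-0.3 rule. From SAP 6.1: at least 25 evaluable at the MTD and at most 50 in total. Assumed, because not stated: the BOIN defaults φ1 = 0.6 × 0.3 = 0.18 and φ2 = 1.4 × 0.3 = 0.42, and elimination when Pr(p > 0.3 | data) > 0.95 under a Beta(1,1) prior.

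**Step 1: reproduce the plan's table.**

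- λe = ln[(1−0.18)/(1−0.3)] / ln[0.3(1−0.18)/(0.18(1−0.3))] = ln(0.82/0.70) / ln(0.246/0.126) = 0.2365.
- λd = ln[(1−0.3)/(1−0.42)] / ln[0.42(1−0.3)/(0.3(1−0.42))] = ln(0.70/0.58) / ln(0.294/0.174) = 0.3585.
- Elimination at n = 9: the posterior probability is 0.953 for 5 DLTs and 0.850 for 4, so the limit is 5.

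All 27 printed escalate, de-escalate and eliminate counts are recovered. The table itself is sound.

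**Step 2: an eliminated dose can be named.** A permitted path is: dose 1 at 0/3 (escalate); dose 2 at 1/3 (stay), 2/6 (stay), 5/9 (eliminate); dose 1 then continues to 1/25. The rates are already ordered, so PAVA leaves them unchanged.

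- Dose 1: |1/25 − 0.3| = |0.040 − 0.3| = 0.260.
- Dose 2: |5/9 − 0.3| = |0.556 − 0.3| = 0.256.

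The literal rule names dose 2. It does not always fail: 2/25 against 5/9 gives 0.220 against 0.256 and names dose 1. Separately, if dose 1 has 3/3 the trial stops, yet dose 1 holds the only estimate (1.0) and the sentence would still name it.

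**Step 3: no unique dose.** With 0/3 and 0/25, both estimates are 0 and both distances 0.300. With 1/6 and 3/25, PAVA pools to (1+3)/(6+25) = 4/31 = 0.129 at both doses.

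**Step 4: against Protocol 5.6.9.** With 0/3 at dose 1 and 10/25 = 0.40 at dose 2, the distances are 0.300 and 0.100, so dose 2 is named although 10/25 lies in the de-escalate row (9 or more of 25). If the table is applied strictly at n = 24, a final 10/25 would go with 0/6 rather than 0/3 at dose 1, which leaves the distances unchanged. With 0/3, the path 8/24 (stay) then 9/25 = 0.36 is permitted; the distances are 0.300 and 0.060, and the conclusion is the same.

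**Step 5: how often.** Trials were simulated from the printed table: start at dose 1, cohorts of 3, stop at 25 on the working dose, 50 in total, or elimination of dose 1; every patient DLT-evaluable; 20,000 trials per scenario. The true DLT rates (dose 1/dose 2) are assumptions.

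| True rates | Eliminated dose 2 named MTD |
|---|---|
| 5%/50% | about 30% |
| 5%/40% | about 20% |
| 10%/40% | 12% |
| 5%/30% | 7% |
| 5%/20% | 1% |
| 5%/10% | under 0.1% |

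| True rates | No unique dose |
|---|---|
| 2%/2% | about 63% |
| 5%/5% | 37 to 38% |
| 5%/10% | 19% |
| 10%/20% | 13% |

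A dose 2 that is not eliminated but has an observed rate of at least 0.3585 is named in 17% of trials at 5%/30% and 24% at 10%/40%.

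**The case against.** **The context implies the exclusion.** SAP 7.7.2 invokes the BOIN principle and SAP 7.8.1 says an eliminated dose is abandoned. Read together, such a dose is arguably not a candidate. That may well be the intent, but the sentence asks for estimates for each dose group and states no restriction, so the exclusion remains an inference.

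**The protocol can break ties.** Protocol 5.6.9 might be used for this. However, SAP 7.7.2 presents its own definition as the one for the study and does not refer to 5.6.9.

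**A reader might infer that the SAP flatly contradicts the protocol.** The documents do not support that. Protocol 5.6.9 leaves its safety criterion undefined and defers to the BOIN assessment, and Protocol 10.1 leaves technical detail to the SAP. De-escalation is a conduct rule under which a dose can be revisited, and only elimination abandons it. When both estimates are below 0.3 and not tied, the closest dose is also the higher one. It is likewise arguable whether supplying a delegated rule is a change that SAP 7.9 had to list.

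**A reader might infer that the headline response result could move to a small cohort.** That is not supported either. SAP 7.1.1 and 7.6.1 report efficacy by dose, SAP 7.6.3 adds a column for all subjects, and safety is by dose group. Nor does the rule steer dosing, which follows the table and the safety meeting.

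**Interim counts are not evidence.** A state such as 1/6 and 5/12 has 18 patients, and 1/6 is in the escalate row, so the trial would continue. The rule applies only at the end of the study.

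**Redaction.** Text is blacked out near the DLT-evaluable definition in SAP 7.7.2 and in SAP 6.4.1.1 and 7.2. A supplementary rule there cannot be excluded, although the MTD sentence itself is complete.

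**Conclusion.** The point holds as a defect in a stated rule. On its visible wording, SAP 7.7.2 can label as MTD a dose the same SAP says is abandoned, and it returns no single dose when the two estimates coincide. It also stands unreconciled with Protocol 5.6.9; that is a difference in definition, not a proven contradiction.

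The size depends on the true DLT rates, which are assumptions. Naming an eliminated dose matters if dose 2 is toxic and dose 1 is not (about 30% of trials at 5%/50%), and it is negligible at 5%/10%. Ties run the other way and are common when both doses are well tolerated. Protocol 2.7 describes these dose levels as safe in earlier trials, though in other combinations, so the low-rate scenarios deserve weight. The percentages also rest on the simplified conduct described above.

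The consequence is confined to the declared MTD and the Protocol 10.1 display for patients treated at it. Results for both doses are reported in any case.

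**What to change.** In SAP 7.7.2:

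1. Search for the estimate closest to 0.3 only among doses that were tested and not eliminated under SAP 7.8.1.
2. State what is reported if the lowest dose is eliminated.
3. Add a tie rule consistent with Protocol 5.6.9, covering both pooled estimates and equal distances on either side of 0.3 (for example 5/25 and 10/25, 0.10 each).

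Then reconcile Protocol 5.6.9 with SAP 7.7.2 and 7.8.1 so that both documents give one definition of MTD, including what counts as safe, and record any resulting change in SAP 7.9. Which definition to adopt is for the sponsor and investigators.

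The cost is a few sentences and a cross-reference, with no extra patients or data. It should be settled before database lock, since a later choice would be made with the DLT counts in view.
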